Study Protocol with Statistical Analysis Plan (SAP)

Title: Evaluation of the Postoperative Effects of Horizontal Platelet-Rich Fibrin after Impacted Third Molar Extraction: A Randomized Controlled Clinical Study

NCT Number: NCT06244797

Last update/approval date: December 28, 2023 (Ethics Committee and Ministry of Health Approval)

1. Background and Rationale

Impacted mandibular third molars are frequently removed due to complications such as pericoronitis, cyst formation, or damage to adjacent teeth. Postoperative sequelae include pain, swelling, and trismus. Platelet-rich fibrin (PRF) is a second-generation platelet concentrate with regenerative and anti-inflammatory potential. Horizontal PRF (H-PRF), produced via horizontal centrifugation, yields higher concentrations of platelets and leukocytes compared with leukocyte PRF (L-PRF). No randomized controlled trial has directly compared H-PRF and L-PRF in mandibular third molar surgery.

2. Study Objectives

Primary Objective: To evaluate whether H-PRF reduces postoperative swelling compared with L-PRF and control.

Secondary Objectives: To compare effects on pain, trismus, soft tissue healing, analgesic consumption, and quality of life (QoL).

3. Study Design

Design: Prospective, randomized, controlled, double-blind clinical trial.

Setting: Tokat Gaziosmanpaşa University, Faculty of Dentistry, Department of Oral and Maxillofacial Surgery.

Duration: Recruitment and follow-up between January and March 2024.

4. Study Population

Inclusion Criteria:

- Patients aged 18–40 years
- Indication for extraction of mucosally retained mandibular third molars
- ASA I classification
- Signed written informed consent

Exclusion Criteria:

- Systemic disease
- Allergy to penicillin or local anesthetics
- Previous radiotherapy to head and neck
- Requirement for antibiotic prophylaxis
- Presence of pericoronitis
- Inability to attend follow-up visits

5. Randomization and Blinding

Randomization performed via sequentially numbered, opaque sealed envelopes prepared by an independent nurse.

Allocation ratio: 1:1:1 (H-PRF, L-PRF, Control).

Patients and outcome assessor blinded.

Operating surgeon aware of allocation.

6. Interventions

H-PRF Group: 10 mL venous blood centrifuged horizontally (2200 rpm, 8 min) and applied to socket.

L-PRF Group: 10 mL venous blood centrifuged via fixed-angle centrifugation (2700 rpm, 12 min).

Control Group: Standard extraction without PRF application.

All sockets closed with 3-0 silk sutures.

Standard postoperative medication: dexketoprofen trometamol (25 mg as needed), chlorhexidine mouth rinse (0.12%, twice daily for 7 days). No prophylactic antibiotics prescribed.

7. Outcomes

Primary Outcome: Swelling (linear facial measurements), assessed pre-op, Day 2, Day 7.

Secondary Outcomes:

- Pain (VAS, 0–100 mm), Days 1–7
- Trismus (maximum interincisal distance), baseline, Day 2, Day 7
- Soft tissue healing (Landry index), Days 2 and 7
- Analgesic consumption (daily record)
- QoL (Majid's questionnaire), Days 4 and 7

8. Statistical Analysis Plan (SAP)

Software: IBM SPSS v23

Normality: Shapiro-Wilk test

Categorical variables: Chi-square test

Continuous variables: One-way ANOVA (normal distribution) or Kruskal-Wallis test (non-normal)

Repeated measures: Repeated measures ANOVA with Bonferroni post hoc (normal) or Friedman with Dunn's post hoc (non-normal)

Baseline imbalance: ANCOVA with baseline covariates (for swelling)

Effect sizes: Mean differences with 95% CI, standardized effect sizes reported

Significance level: $p < 0.05$

Missing data: No missing data expected (all 75 randomized completed)

9. Ethical Considerations

Approved by Tokat Gaziosmanpaşa University Clinical Research Ethics Committee (Approval No: 23-KAEK 146).

Additional authorization: Ministry of Health (Decision No: E-57955685-000-224940348).

Registered at ClinicalTrials.gov (NCT06244797).

Written informed consent obtained from all participants.

10. Data Handling

Data anonymized and stored securely.

Analyses conducted according to pre-specified protocol.

Data available upon reasonable request from corresponding author.

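### No harms outcome is planned, so complications such as dry socket or infection cannot be reported systematically by arm

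*Combined protocol and SAP*

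**What the plan says.** **Outcomes.** Section 7 opens with "Primary Outcome: Swelling (linear facial measurements), assessed pre-op, Day 2, Day 7". The secondary outcomes are pain on a visual analogue scale, mouth opening, "Soft tissue healing (Landry index), Days 2 and 7", a daily analgesic record and a quality-of-life questionnaire. Section 2 names the same six domains and has no safety objective. Section 8 has no safety analysis.

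**Treatment of the socket.** For H-PRF, Section 6 says "10 mL venous blood centrifuged horizontally (2200 rpm, 8 min) and applied to socket". The L-PRF line describes centrifugation only and does not say where the product goes. The control arm has an extraction without PRF.

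**Antibiotics.** The standard medication common to all arms ends with "No prophylactic antibiotics prescribed". The exclusions in Section 4 include "Requirement for antibiotic prophylaxis" and "Presence of pericoronitis".

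**Size and status.** Section 5 gives "Allocation ratio: 1:1:1 (H-PRF, L-PRF, Control", and Section 8 gives "No missing data expected (all 75 randomized completed".

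**The concern.** Dry socket, infection, bleeding, adverse events, unplanned antibiotics and unscheduled visits appear nowhere in the objectives, outcomes, SAP, ethics or data-handling sections. Complications are mentioned once, in Section 1, as a reason for removing the teeth. Followed as written, the plan therefore yields no harm data by arm.

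The arms differ in whether a product is placed in the wound, so a reader of the results will ask whether complications differed too. A report could favour H-PRF on swelling and have no planned harm data to set beside that benefit. A complication, or the drugs used to treat it, may also affect Day 7 swelling, pain and mouth opening. If the event is not recorded, the report cannot describe whether a Day 7 difference is spread across the arm or comes partly from a few affected patients.

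**Working it through.** The plan states no figure on this point, so there is nothing to reproduce. The check has two parts.

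**1. Does any listed outcome identify a complication?**

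- Landry index, Days 2 and 7: the nearest candidate, but the documents derive no diagnosis of dry socket or infection from it.
- Pain, Days 1 to 7, and quality of life, Days 4 and 7: a severe complication could show in the scores, but the scores do not say what caused them.
- Analgesic record: the only drug use collected as an outcome. A course of antibiotics would leave no planned record.

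None of them does.

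**2. What could a harms outcome show at this sample size?**

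Inputs: 75 randomized (Section 8) and 1:1:1 allocation (Section 5). This gives 75 / 3 = 25 per arm if the allocation is exactly balanced; the documents do not state the arm size. Complication rates p are assumptions.

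Chance of at least one event among n patients: 1 − (1 − p)^n.

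| Assumed rate p | Expected events per arm, 25p | At least one in 25 | At least one in 75 |
|---|---|---|---|
| 2% | 0.5 | 1 − 0.98^25 = 39.7% | 1 − 0.98^75 = 78.0% |
| 5% | 1.25 | 1 − 0.95^25 = 72.3% | 1 − 0.95^75 = 97.9% |
| 10% | 2.5 | 1 − 0.90^25 = 92.8% | 1 − 0.90^75 > 99% |

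Upper limit of the exact (Clopper-Pearson) two-sided 95% interval when no event is seen: 1 − 0.025^(1/n).

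- n = 25: 1 − 0.025^(1/25) = 13.7%.
- n = 50 (the two PRF arms pooled): 1 − 0.025^(1/50) = 7.1%.

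Power to compare two arms of 25 (two-sided 5% level, assumed because Section 8 does not state sidedness):

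- 5% against 20%: about 36%; 76 per arm would be needed for 80% power.
- 10% against 30%: about 42%; 62 per arm would be needed.

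So events are likely to occur somewhere in the trial, but a test between arms would be uninformative. Descriptive reporting is what the numbers support.

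**Scale of a contribution to swelling (assumed values).** If k patients of 25 each swell by an extra 2 SD, the arm mean moves by 2k / 25 SD: 0.08 SD for one patient and 0.24 SD for three. This shows only that a few patients can matter at this size. It is not evidence that they did.

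**The case against.** Several stronger readings are tempting, and the documents do not support them.

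- **That unrecorded complications invalidate the swelling comparison.** Complications arise after randomization, so any swelling they cause is part of each arm's total effect. The comparison of mean swelling is not confounded. Recording the events would not separate complication-driven swelling from treatment effect either, because affected patients are a subset formed after randomization. Listing their values can only describe.
- **That the antibiotic policy is at fault.** It is the same in every arm and cannot bias the comparison. Patients who need prophylaxis or have pericoronitis are excluded, only ASA I patients enter, and everyone receives a week of chlorhexidine rinsing. The policy makes a record of infection more relevant and has no further bearing here.
- **That two arms are stated to receive a product in the socket.** Only the H-PRF line says so. For L-PRF it is a likely inference.
- **That the trial can say nothing about harm.** The document is a brief summary, and staff may note complications in the clinical record. Pain, analgesic use and the Landry score could also reflect a severe one. What the text does show is that no harm is defined or planned for collection.

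Two further objections stand. The percentages above rest on assumed rates and give the chance that an event occurs, not the size of any distortion. And Section 8 speaks of all 75 patients as having completed, although the document is dated 28 December 2023 and Section 3 places recruitment and follow-up in January to March 2024. If follow-up is over, nothing can be added at the visits.

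The core survives: no objective, outcome or analysis covers harms, and no listed outcome stands in for one.

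**Conclusion.** The point holds as a gap in measurement and should be addressed. The plan collects no defined harm, so complications cannot be reported systematically by arm, and the contribution of affected patients to a Day 7 difference cannot be described. The primary randomized comparison is unaffected.

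The size depends on a complication rate that the documents do not give. Over an assumed range of 2% to 10% with 25 per arm, the chance of at least one case is 40% to 93% in a given arm and 78% to over 99% in the whole trial. Even with complete recording the safety information would be modest, since an arm with no events is still compatible with a true rate of up to 13.7%.

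**What to change.** **If patients are still being followed.** Add a descriptive safety outcome to Section 7 with four components, each with a definition written by the investigators before data are seen:

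1. dry socket;
2. surgical-site infection;
3. bleeding needing an unplanned visit;
4. any antibiotic or other non-protocol drug taken up to Day 7.

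The blinded assessor records all four at the existing Day 2 and Day 7 visits.

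Add to Section 8: counts by arm with exact 95% confidence intervals and no hypothesis test; all patients stay in the primary analysis whether or not a complication occurs; swelling values of affected patients are listed by arm as description only.

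**If follow-up is complete.** Extract the same events from clinical records, by arm, and label them as not prespecified. If the records do not allow this, state in the report that harms were not systematically collected.

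The sponsor should say which situation applies. Section 6 should also state where L-PRF is placed.

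**Cost.** In the first case, a few extra items on forms at visits already planned, and one table. In the second, a review of 75 records, with the risk that events were noted unevenly. In both, estimates are imprecise at about 25 per arm, and events after Day 7 are not captured. No change to any treatment is proposed.

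### The SAP does not say which day or model term decides the primary swelling question, or whether one or both H-PRF contrasts must succeed, and its non-normal branch names no pairwise between-arm test

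*Combined protocol and SAP*

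**What the plan says.** Section 2 of the combined protocol and SAP states the question: "Primary Objective: To evaluate whether H-PRF reduces postoperative swelling compared with L-PRF and control". That is two between-arm contrasts. Section 7 gives the endpoint: "Primary Outcome: Swelling (linear facial measurements), assessed pre-op, Day 2, Day 7". It names no primary day and no single swelling value.

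Section 8 lists tests by type of data and assigns none to the primary outcome:

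- Branch rule: "Normality: Shapiro-Wilk test". The data to be tested (arm, day, change or residual) are not given.
- Continuous data: "Continuous variables: One-way ANOVA (normal distribution) or Kruskal-Wallis test (non-normal". No pairwise follow-up is given.
- Repeated data: "Repeated measures: Repeated measures ANOVA with Bonferroni post hoc (normal) or Friedman with Dunn's post hoc (non-normal". No model term is named, and the target of the Bonferroni comparisons (arms or times) is not stated.
- Swelling in particular: "Baseline imbalance: ANCOVA with baseline covariates (for swelling".
- Estimation: "Effect sizes: Mean differences with 95% CI, standardized effect sizes reported". No pair or day is named.

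The significance level is 0.05, with no sidedness and no division across days or contrasts. Section 10 says that the analyses follow a pre-specified protocol.

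**The concern.** A reader who follows section 8 exactly can finish without a named test of either H-PRF contrast. A significant three-arm test does not fill the gap, because it can arise from a difference that does not involve H-PRF.

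The result called primary could be Day 2, Day 7, the group term or the group-by-time term. It could be adjusted for pre-op swelling or not, since ANCOVA is tied to baseline imbalance and its use can therefore depend on the data. Success could mean one contrast or both. If these choices are made once results are visible, the nominal 0.05 no longer describes the chance of a false primary claim, and the statement in section 10 cannot be checked for the primary outcome.

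**Working it through.** **Inputs from the documents.** 75 randomized (section 8, missing-data line) at 1:1:1 (section 5), so 75/3 = 25 per arm. Two contrasts (section 2), two post-operative days (section 7), level 0.05 (section 8). The documents give no power, SD, target effect or error rate for several looks, so there is no figure of theirs to reproduce.

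**Assumptions.** Two-sided tests, normal data, equal spread, and Day 2/Day 7 correlation from 0 to 0.8.

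**Step 1: what each line can decide.**

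| SAP line | Compares arms? | Pairwise arm test named? | Day, term or success rule? |
|---|---|---|---|
| One-way ANOVA / Kruskal-Wallis | Yes, all three together | No | No |
| Repeated measures ANOVA, Bonferroni | Possible | Not clear (arms or times) | No |
| Friedman, Dunn's | No, times within patients | No | No |
| ANCOVA | Possible | No | No; only under baseline imbalance |
| Mean differences, 95% CI | Possible | Estimate only, no pair named | No |

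In the non-normal branch the only between-arm test is Kruskal-Wallis, which is omnibus.

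**Step 2: either day counts, arms equal.** The omnibus test is the F-test on 2 and 72 df. Each H-PRF contrast is t = (difference in means)/√(MSW × 2/25) on 72 df, where MSW is the pooled within-arm mean square. The gated version requires F significant at 0.05 on that day and the contrast significant at 0.05. The Bonferroni version uses 0.05/3 = 0.0167 for each of three pairs within each day. As a check, two independent days give 1 − 0.95² = 9.75% for the omnibus test. Simulated results, 100,000 trials per row:

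| Day 2/Day 7 correlation | Omnibus, either day | False H-PRF contrast, gated | False H-PRF contrast, Bonferroni(3) |
|---|---|---|---|
| 0 | 9.7% | 8.2% | 6.0% |
| 0.3 | 9.4% | 7.9% | 6.0% |
| 0.5 | 9.0% | 7.7% | 5.8% |
| 0.8 | 7.8% | 6.6% | 5.0% |

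With one named day, the gated false H-PRF contrast is 4.1% to 4.2%.

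**Step 3: repeated measures ANOVA, either term counts.** With three arms and three times, the group term has 2 and 72 df and group-by-time has 4 and 144 df. At correlations 0, 0.5 and 0.8, each term alone rejects in about 5% of trials. Counting either gives 9.9%, 9.9% and 9.8%, again close to 1 − 0.95² = 9.75%.

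**Step 4: a single fixed rule.** ANCOVA of one day's swelling on arm and pre-op swelling has 75 − 4 = 71 residual df. Testing two contrasts at 0.05/2 = 0.025 each gives a false H-PRF claim in about 4.7% of trials when arms are equal. If H-PRF is better than both other arms by an assumed number of SDs:

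| Assumed advantage | At least one won (pre-op correlation 0 / 0.5) | Both won (0 / 0.5) |
|---|---|---|
| 0.5 SD | 45% / 56% | 16% / 24% |
| 0.8 SD | 84% / 93% | 56% / 73% |
| 1.0 SD | 96% / 99% | 81% / 93% |

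**The case against.** The best defence is that the plan is less open than it looks. Section 2 does name the two contrasts. ANCOVA is linked to swelling. Repeated measures ANOVA can take all times together. Mean differences with confidence intervals are promised whatever the distribution. Dunn's is a usual follow-up to Kruskal-Wallis and may have been meant for it. The SAP also names Bonferroni, and applying it to arm pairs within each day brings the false H-PRF rate down to about 6% to 5%, at most about one point above nominal.

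Much of this stands. A reader might infer that the contrasts are undefined, or that the non-normal branch offers no between-arm comparison of pairs at all. Neither is right: the contrasts are named, and pairwise estimates could be produced. What is absent is a named pairwise test, a day, a term and a success rule.

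A reader might also infer that this trial runs at a 10% error rate. The documents do not support that, because the 8% to 10% figures need an either-day or either-term rule that the SAP nowhere states. Nor does the SAP propose Friedman for comparing arms. A significant Friedman result when swelling changes over time is a correct finding about time, not a false positive.

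Lastly, the missing-data line reads "Missing data: No missing data expected (all 75 randomized completed", from which a reader might infer that the analysis was chosen with results in view. The line speaks of completion. It does not show that anyone had seen outcomes when the tests were listed.

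**Conclusion.** The point holds and should be fixed. The contrasts are given, but section 8 fixes neither the deciding day nor the deciding term, does not say whether one or both contrasts must succeed, and names no pairwise between-arm test in the non-normal branch. Use of the pre-op value is left conditional on imbalance.

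The inflation ranges from almost none to about double the nominal level, depending on which open reading is adopted: about 5% to 6% with Bonferroni within each day, about 6.6% to 8% after the omnibus test, and about 8% to 10% for the omnibus test itself or for either repeated-measures term. These figures assume 25 per arm, normal data of equal spread and the stated correlations. They measure latitude, not an error rate that the plan adopts. The textual gap does not depend on them. The trial data remain usable; what cannot be supported as written is calling the primary swelling conclusion pre-specified.

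**What to change.** Add a short primary-analysis paragraph to section 8:

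- Name one primary day (the sponsor's choice) and define how the linear measurements become one swelling value per patient and day.
- Primary analysis: ANCOVA of that day's swelling on arm and pre-op swelling, used whether or not baselines differ and whatever Shapiro-Wilk shows.
- Test H-PRF against L-PRF and H-PRF against control, each at 0.025 two-sided (Bonferroni, which the SAP already names), with estimates and confidence intervals. State that each contrast is claimed separately.
- Treat the other day as supportive.
- As a sensitivity analysis, report Kruskal-Wallis on change from pre-op, with between-arm Dunn's for the same two contrasts.
- Use Friedman only for change over time within patients.
- If outcome data have been seen, date the choice and label it post hoc.

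The cost is wording, with no extra patients. An effect seen only on the other day would not be primary, and splitting the level limits power at small effects, as the last table under the working shows. The rank analysis of change can be much weaker than ANCOVA when pre-op swelling predicts little: at pre-op correlation 0 with Dunn's at 0.025, both contrasts are won in about 5%, 20% and 37% of trials at 0.5, 0.8 and 1.0 SD. A non-significant sensitivity result would therefore not by itself contradict the primary one. If results are already known, the new wording makes the analysis transparent but cannot make it pre-specified.

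### A normality pre-test picks the primary swelling test, neither candidate uses the pre-operative measurement, and on the rank branch the p-value and the confidence interval answer different questions

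*Combined protocol and SAP*

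**What the plan says.** Section 7 defines the primary endpoint: "Primary Outcome: Swelling (linear facial measurements), assessed pre-op, Day 2, Day 7". Section 2 sets the comparison: "Primary Objective: To evaluate whether H-PRF reduces postoperative swelling compared with L-PRF and control".

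Four lines of section 8 then bear on how swelling is tested and reported:

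- The gate: "Normality: Shapiro-Wilk test". Its level is not given. Nor is it said whether it is applied to raw values, changes or residuals, by arm or pooled, or at which visit.
- The between-arm test that depends on the gate: "Continuous variables: One-way ANOVA (normal distribution) or Kruskal-Wallis test (non-normal". A second gated pair covers repeated measures: "Repeated measures: Repeated measures ANOVA with Bonferroni post hoc (normal) or Friedman with Dunn's post hoc (non-normal".
- The only mention of baseline: "Baseline imbalance: ANCOVA with baseline covariates (for swelling". Nothing says what sets it off, whether it is the primary analysis, or whether it still applies when the gate reports non-normality.
- The effect measure: "Effect sizes: Mean differences with 95% CI, standardized effect sizes reported". No alternative is given for the rank branch.

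**The concern.** Swelling is a continuous outcome, so the gate applies to it. Which test decides the primary objective is therefore unknown until the data have been looked at, and the choice could differ between Day 2 and Day 7. The ANCOVA line does not settle this. Under its heading it reads as a second choice that depends on the data.

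Two things follow. First, if Kruskal-Wallis is selected, the p-value concerns rank ordering while the reported interval concerns a difference in means. A significant p-value can then sit beside an interval that includes zero, or the reverse, and the plan does not say which governs. Second, the pre-operative measurement is collected on every patient, yet neither gated test as listed has a baseline term. Precision that the trial has already paid for may go unused on either branch.

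**Working it through.** **Inputs from the documents.** Section 8 speaks of 75 randomized and section 5 gives 1:1:1, so 75/3 = 25 per arm if the arms are equal. The significance level is 0.05 (section 8). There is no sample-size calculation, power, SD or effect size, so the plan has no figure to reproduce.

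**Assumptions.** Shapiro-Wilk is run at 0.05 in each arm, and any failing arm sends the comparison to Kruskal-Wallis. One arm is shifted by 0.5 SD unless stated. Outcomes are normal, or lognormal with the log-SD given. Pre/post correlation r is 0.5, 0.7 or 0.9.

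**1. How often chance alone switches the test.** With exactly normal data the rate is 5% per arm. For at least one of three arms at one visit it is 1 − 0.95³ = 14.3%; simulation gave 13–16%. A single test on pooled residuals would give 5%. If visits are gated separately and treated as independent, Day 2 and Day 7 take different routes with probability 2 × 0.143 × 0.857 = 24.5%; positive correlation between visits lowers this.

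The gate also misses real skew. At log-SD 0.3 one arm is flagged 31% of the time and at least one of three about 65–68%, so about a third of such trials would still go to ANOVA. At log-SD 0.5, 95% are flagged.

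**2. Disagreement between p-value and interval.** This compares the pairwise rank test at 0.05 with the t-based 95% CI for the mean difference, in trials that the gate flags.

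| Setting | Disagree on significance |
|---|---|
| 0.5 SD, normal | about 8–12% |
| 0.5 SD, log-SD 0.3–0.5 | about 11–18% |
| 0.8 SD, normal | 7.8% |
| 0.8 SD, log-SD 0.5 | 12.8% |
| 0.8 SD, log-SD 1.0 | 16.6% |
| No effect, all three distributions in the 0.8 SD rows | 3.1–4.5% |

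These rates are conditional on a flag. For normal data, as a share of all trials, the first row is 0.15 × 8% to 0.15 × 12%, or 1.2–1.8%.

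**3. What the baseline term is worth.** For arm means 0, 0 and 0.5 SD, the sum of squared deviations from the grand mean is 2(1/6)² + (1/3)² = 0.1667. The noncentrality is λ = 25 × 0.1667/(1 − r²), with r = 0 for one-way ANOVA. Power is the upper tail of the noncentral F beyond the 5% critical value, on 2 and 72 degrees of freedom for ANOVA and 2 and 71 for ANCOVA.

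| Analysis | λ | Power, formula | Power, simulation |
|---|---|---|---|
| One-way ANOVA | 4.17 | 41.5% | 40–43% |
| ANCOVA, r = 0.5 | 5.56 | 53% | 55% |
| ANCOVA, r = 0.7 | 8.17 | 71% | 70% |
| ANCOVA, r = 0.9 | 21.93 | 99% | 99% |
| Kruskal-Wallis, post-operative value | – | – | 38–41% |

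With normal data, moving from ANOVA to Kruskal-Wallis costs only 2–3 points. Most of the gap to ANCOVA is the baseline term.

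**4. Where ANCOVA loses.** In flagged trials with a 0.5 SD shift:

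| log-SD | r | Kruskal-Wallis | ANCOVA |
|---|---|---|---|
| 0.5 | 0.5 | 59% | 53% |
| 0.5 | 0.7 | 59% | 67% |
| 0.8 | 0.5 | 87–88% | 57% |
| 0.8 | 0.7 | 88% | 70% |

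**5. Type I error of the two-stage rule.** In 4,000 simulated trials per setting: 4.8% (normal), 4.5% (log-SD 0.5) and 5.0% (log-SD 1.0).

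**The case against.** The strongest reply has four parts.

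- **The plan does name ANCOVA for swelling.** True, so swelling is not left with unadjusted tests alone. But the line has no trigger, no rank and no stated relation to the gate, so it does not fix the primary analysis.
- **The gate is not what costs precision.** This stands. One-way ANOVA lacks the baseline term just as Kruskal-Wallis does. Ranks could also use baseline through change scores: Kruskal-Wallis on change has 40%, 61% and 98% power at r = 0.5, 0.7 and 0.9. The plan does not specify change scores.
- **A reader might infer that precision is lost whenever the rank route is taken.** That does not hold. Under strong skew with moderate correlation the rank test has clearly more power than ANCOVA.
- **The harm is modest.** A reader might infer that the pre-test inflates false positives or often rejects truly normal data. Neither is supported: type I error stayed at 4.5–5.0%, and the false flag rate is 5% per arm, about 15% for any of three. The disagreement rates also rest on assumed distributions, and strong skew may be unlikely for raw facial distances.

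What survives is that the primary test is not fixed and that the rank branch has no matching effect measure. Both can be read from section 8 without any simulation.

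**Conclusion.** The point holds. Section 8 does not commit to one primary analysis of swelling, does not secure use of the pre-operative value, and can pair a rank p-value with a mean-difference interval. Under the stated assumptions, a chance switch affects about 15% of trials with normal data at a given visit (5% with one pooled residual test). Disagreement in flagged trials is roughly 8–18% at a 0.5 SD shift. The power gain from ANCOVA runs from modest at r = 0.5 to very large at r = 0.9 when data are near normal, and it reverses under strong skew. The true SD, shape and correlation of swelling are not in the documents, so these figures indicate scale only. This is a problem of pre-specification and coherent reporting, not of false-positive control.

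**What to change.** Rewrite the section 8 entry for swelling as follows:

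- Swelling at each post-operative visit is analysed by ANCOVA with arm and the pre-operative measurement, whatever Shapiro-Wilk or a baseline comparison shows.
- Adjusted mean differences, 95% CIs and p-values all come from that one model.
- The standard-error method is fixed in advance, for example bootstrap CIs and p-values in all cases. Choosing it after inspecting residuals would bring back a data-driven step.
- Kruskal-Wallis on change from pre-op is a sensitivity analysis only.
- Where a rank test is the method for a secondary outcome, such as the Landry index, a Hodges-Lehmann difference with its CI replaces the mean difference.

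This does not by itself choose between Day 2 and Day 7 or name a primary contrast; those still have to be stated. The cost is SAP wording and one extra analysis, with no new data collection. The downside is some lost power if swelling is strongly skewed, which the rank sensitivity analysis would show. Because section 8 already describes all 75 patients as having completed, the revision should be dated and should say whether outcome data had been seen.

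### Section 8 does not say whether the pre-op value of swelling and trismus is a response or a covariate; one permitted analysis dilutes the arm difference by one third, another discards the baseline

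*Combined protocol and SAP*

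**What the plan says.** Section 7 (Outcomes) gives the primary outcome as "Primary Outcome: Swelling (linear facial measurements), assessed pre-op, Day 2, Day 7" and one secondary outcome as "Trismus (maximum interincisal distance), baseline, Day 2, Day 7". Each therefore has three assessments, of which one precedes treatment.

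Section 8 (Statistical Analysis Plan) has three lines that could apply to these outcomes:

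- One line covers any measurement on a continuous scale, with no visit named: "Continuous variables: One-way ANOVA (normal distribution) or Kruskal-Wallis test (non-normal".
- A separate line deals with outcomes measured at several visits, again without naming them: "Repeated measures: Repeated measures ANOVA with Bonferroni post hoc (normal) or Friedman with Dunn's post hoc (non-normal".
- The only line that brings in the pre-op value is restricted to the primary outcome: "Baseline imbalance: ANCOVA with baseline covariates (for swelling".

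Section 8 also promises "Effect sizes: Mean differences with 95% CI, standardized effect sizes reported", without naming a visit or an average over visits. None of these lines says which visits form the repeated factor, whether arm is a factor in that model, whether arms are compared on a main effect or an arm-by-time term, or whether the post hoc tests compare arms or visits. No line provides baseline adjustment for trismus.

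**The concern.** The primary objective in Section 2 concerns swelling after surgery, compared between arms. A value taken before surgery cannot carry a treatment effect. It can do harm if it is averaged into the response, it can be ignored, or it can sharpen the comparison as a covariate. Section 8 permits all three for swelling and, as written, only the first two for trismus.

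A default three-level repeated-measures run with Bonferroni comparisons of arm marginal means would report a shrunken arm difference. Per-visit one-way ANOVA would report an undiluted but less precise one. In either case a real reduction in swelling or trismus could be missed although the trial already collects the measurement that would help to detect it.

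**Working it through.** **Plan's own figure.** The documents give no sample-size calculation, effect size, SD or power, so there is nothing to reproduce.

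**Inputs from the documents.** Three assessments per outcome, one of them before treatment (Section 7); "Allocation ratio: 1:1:1 (H-PRF, L-PRF, Control") (Section 5); 75 patients randomised and a 0.05 significance level (Section 8). An even split gives 75/3 = 25 per arm.

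**Assumptions, not in the documents.** SD 1 at every visit; equal correlation r between visits, 0.5 to 0.8; arm effects d2 = d7 = 0.8 SD on Days 2 and 7; two-sided alpha 0.05/3 for three arm pairs; SD pooled over the three arms.

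**Step 1: dilution (needs no assumed SD or correlation).** Randomisation makes the expected pre-op difference zero.

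- Three-visit average: (0 + d2 + d7)/3.
- Postoperative average: (d2 + d7)/2.
- Ratio: (1/3)/(1/2) = 2/3, a loss of exactly one third whenever the postoperative average is non-zero.

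Against a single visit the loss depends on the pattern. If d7 = d2 it is 33%. If d7 = d2/2 it is 50% against Day 2 and zero against Day 7. If d7 = 0 it is 67% against Day 2. If d7 = d2/4, the three-visit figure is 1.25 × d2/3 = 0.417 × d2, which overstates Day 7 by 67%.

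**Step 2: power for one arm pair.** The noncentrality is effect/√(2V/25), where V is the between-patient variance of the quantity analysed. There are 72 degrees of freedom without the covariate and 71 with it.

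| Quantity compared | Effect | V | V at r = 0.5; 0.8 | Power at r = 0.5; 0.8 |
|---|---|---|---|---|
| Three-visit average | 0.533 | (1+2r)/3 | 0.667; 0.867 | 45%; 34% |
| Day 2, raw | 0.8 | 1 | 1; 1 | 65%; 65% |
| Two-visit postoperative mean, raw | 0.8 | (1+r)/2 | 0.75; 0.90 | 79%; 70% |
| Day 2, pre-op as covariate | 0.8 | 1 − r² | 0.75; 0.36 | 79%; 99% |
| Two-visit postoperative mean, pre-op as covariate | 0.8 | (1+r)/2 − r² | 0.50; 0.26 | 94%; over 99% |

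Example at r = 0.5: the three-visit average gives 0.533/√(2 × 0.667/25) = 2.31, and the postoperative mean with covariate gives 0.8/√(2 × 0.50/25) = 4.00.

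**Step 3: the arm-by-time term.** This was simulated with 3,000 replicates, three arms, three visits, one arm differing, overall tests at 0.05 and d2 = 0.8 SD. At r = 0.5 with d7 = 0.8 SD, power was 87% for the interaction and 65% for the arm main effect over three visits. With d7 = 0 it was 87% and 20%. At r = 0.8 the interaction had at least 99% power for d7 = 0, 0.4 and 0.8 SD. The dilution therefore affects the main effect and not the interaction.

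**The case against.** The strongest reply is that Section 8 never says the pre-op value is a response level or that arms are compared on a main effect. A competing reading fits the text at least as well. The Friedman test has no between-arm factor, and it is offered as the non-normal counterpart of repeated-measures ANOVA. That suggests this line describes change over visits within an arm, with arms compared by the separately listed one-way ANOVA or Kruskal-Wallis test. On that reading no arm effect is averaged over the pre-op visit. Even in a three-visit model, the interaction is undiluted and arm differences could be taken at each visit. For swelling, a baseline ANCOVA is also on the list.

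Most of this stands, and it rules out three stronger conclusions that a reader might draw:

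- *That the plan prescribes a diluted analysis.* It does not; dilution follows from one permitted choice.
- *That the effect is understated by at least one third.* The loss is exactly one third against the postoperative mean. It is a lower bound only against the larger of two same-direction visit effects.
- *That trismus is left with the repeated-measures model alone.* Interincisal distance is continuous, so the one-way line covers it too.

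The competing reading does not remove the loss, however. It exchanges dilution for an unadjusted comparison: 65% power on raw Day 2, against 79% to 99% with the covariate. The swelling ANCOVA is tied to baseline imbalance, and its relation to the other tests is not stated. The interaction is a 4-df overall test, (3 − 1) × (3 − 1), and does not by itself give the H-PRF versus L-PRF or H-PRF versus control estimate.

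**Conclusion.** The point holds as a gap in specification with a measurable cost on either reading. It does not show that a biased analysis was planned.

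If pre-op is a third time level and arms are compared on the main effect, the expected difference is one third below the postoperative mean. That result is algebra and rests only on randomisation. If arms are compared visit by visit without adjustment, the estimate is undiluted but baseline information is thrown away. Trismus has no listed remedy for this, and swelling has one only under the imbalance heading.

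The power figures are illustrations. They rest on an even split, equal SDs and correlations, a 0.8 SD effect on both days and the Bonferroni level used above. If the effect fades by Day 7, power on either average falls. The covariate's advantage over the raw comparison grows with the correlation between the pre-op and later values, which the documents do not give.

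**What to change.** For both swelling and trismus, state in Section 8 that Day 2 and Day 7 are the repeated responses, and that the pre-op value is a covariate in all cases, not only when arms look imbalanced. The model terms are arm, day and arm-by-day. Report adjusted mean differences with 95% CI for H-PRF versus L-PRF and H-PRF versus control at each day. Do not base any arm comparison on an average that includes the pre-op visit.

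The cost is one SAP sentence and one degree of freedom (72 to 71), with the same data and no new measurements. Because Section 8 already reports that all 75 patients completed, the change should be dated and its timing relative to the analysis recorded.
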